11.3 Clinical Laboratory Adverse Events

The investigator is responsible for reviewing the results of all laboratory tests as they become available and determining whether an abnormal value in an individual subject is a clinically significant change from the subject's baseline value(s). The investigator may repeat the laboratory

test or request additional tests to verify the results of the original laboratory tests. In general, abnormal laboratory findings without clinical significance (based on the investigator's judgment) are not to be recorded as AEs. However, laboratory value changes that require treatment or adjustment in current therapy are to be considered AEs. When applicable, clinical sequelae (not the laboratory abnormality) are to be recorded as the AE.

11.4 Serious Adverse Events

A *serious adverse event* (SAE) is defined as any AE occurring at any dose that results in any of the following outcomes:

- Death
- Life-threatening AE (Note: A life-threatening AE is one that, in the view of the investigator places the subject at immediate risk of death from the reaction as it occurred)
- Hospitalization or prolongation of existing hospitalization
- A persistent or significant disability/incapacity
- A congenital anomaly/birth defect.

Important medical events that may not result in death, be life threatening, or require hospitalization may be considered an SAE when, based upon appropriate medical judgment, they may jeopardize the subject and may require medical or surgical intervention to prevent one of the outcomes listed in this definition. Examples of such medical events include blood dyscrasias or convulsions that do not result in subject hospitalization, or the development of drug dependency or drug abuse.

An *unexpected AE* is defined as any adverse event for which the specificity or severity is not consistent with the AE profile in the current EQ001 Investigator's Brochure.

All SAEs, regardless of cause(s) or causal relationship to study drug, must be reported within 24 hours to the study Sponsor and/or designee.

11.5 Reporting Adverse Events

11.5.1 Reporting Procedures for Nonserious Adverse Events

The investigator is responsible for ensuring that all AEs observed by the investigator or designee or reported by the subject are reported using the AE eCRF.

The investigator will assign the following AE attributes:

- AE diagnosis or syndrome(s), if known (if not known, signs or symptoms)
- Dates of onset and resolution (if resolved)

Equillium AUS Pty Ltd	Clinical Study Protocol No. EQ001-19-001	Page 56 of 79
-----------------------	--	---------------

- Severity
- Causality relationship to study drug or study-related procedures
- Action taken
- Outcome

Follow-up of nonserious AEs will continue through the last day on the study and/or until a definitive outcome (eg, resolved, resolved with sequelae, lost to follow-up) is achieved.

When a subject is withdrawn from the study because of a nonserious AE, the Sponsor and/or designee must be notified by email or phone within 48 hours.

11.5.2 Reporting Procedures for Serious Adverse Events

The investigator is responsible for ensuring that all SAEs observed by the investigator or reported by the subject are promptly assessed and reported to the Sponsor and/or designee. The investigator must assess the causality relationship of the SAE to study drug or any study-related procedure.

The procedures for reporting SAEs are as follows:

- Record the SAE on the AE eCRF and complete the Serious Adverse Event Report form.
- Within 24 hours of the investigator's knowledge of the event, enter via the eCRF the SAE Report form to the attention of the Sponsor and/or designee. Additional contact numbers and AE/SAE reporting instructions will be provided in the Study Manual.
- For fatal or life-threatening events, also email and/or fax redacted copies of hospital case reports, autopsy reports, and other documents, when requested and applicable. Transmission of such documents should occur with personal subject details de-identified, without losing the traceability of a document to the subject identifiers. Transmission of the initial report of the event should not be delayed in order to include these additional documents.
- The Sponsor or/or designee may request additional information from the investigator to ensure the timely completion of accurate safety reports.

The investigator must take all necessary therapeutic measures for resolution of the SAE. Any medications or therapies necessary for treatment of the SAE must be recorded in the event description section of the SAE form and the concomitant medication eCRF.

Follow-up of SAEs will continue through the last day on the study and/or until a definitive outcome (eg, resolved, resolved with sequelae, lost to follow-up, fatal) is achieved.

While pregnancy is not considered an AE, all cases of fetal drug exposure via a maternal parent as study subject or pregnancy of a partner of a male study subject will be reported immediately to

the Sponsor or its designee. Information related to the pregnancy must be documented on a Pregnancy Confirmation and Outcome Form, provided by the Sponsor or its designee, and the pregnancy should be followed until a definitive outcome has been determined.

The Sponsor or its designee will report SAEs as required to regulatory authorities and investigators in compliance with all reporting requirements, according to local regulations and International Council for Harmonisation (ICH) Good Clinical Practice (GCP).

The investigator will notify the appropriate Independent Ethics Committee (IEC) of SAEs occurring at the study site and other AE reports received from the Sponsor, in accordance with local requirements. The investigator or designee at each study site is responsible for submitting safety reports (initial and follow-up) and other safety information (eg, in the revised [EQ001 Investigator's Brochure](#)) to the IEC and/or other applicable regulatory authorities for retaining a copy in the study files.

For more information, contact the Office of the Vice President for Research and Economic Development at [contact] or [contact].

For more information, contact the Office of the Vice President for Research and Economic Development at [contact] or [contact].

For more information, contact the Office of the Vice President for Research and Economic Development at [contact] or [contact].

© 2013 Pearson Education, Inc.

the *Journal of the American Statistical Association* (1980, 75, 311-322) and the *Journal of the Royal Statistical Society, Series B* (1981, 43, 1-37). The latter paper is the most comprehensive treatment of the topic, and it is the source of the following summary. The reader is referred to that paper for a detailed treatment of the topic.

13 PLANNED STATISTICAL METHODS

A detailed description of data analysis and statistical methods to be used will be outlined separately in the SAP.

13.1 General Considerations

Data will be summarized using descriptive statistics (n, mean, median, standard deviation, minimum, maximum) for continuous variables and frequencies and percentages for discrete variables. All data summaries will be displayed by cohort and by treatment group (EQ001 or placebo). A total column for treated cohorts separated by treatment group will also be included. Baseline values of variables are considered the last available non-missing value prior to receiving any study drug. By-subject listings of the data will also be provided. All data summaries and listings will be produced using the SAS® software, version 9.3 or higher.

[REDACTED]

[REDACTED]

[REDACTED]

[REDACTED]

[REDACTED]

13.3 Analysis Populations

13.3.1 Safety Population

The *safety population* consists of all subjects who receive any study drug.

13.3.2 Pharmacokinetic Analysis Population

The *pharmacokinetics population* consists of those subjects in the safety population who have at least 1 measurable post-EQ001 exposure concentration.

[REDACTED]

[REDACTED]

[REDACTED]

13.3.4 Efficacy Population

The *efficacy population* consists of those subjects in the safety population who have at least 1 post-treatment clinical activity assessment.

13.4 Subject Disposition

Subject disposition data will be summarized and will include the number and percent of enrolled subjects; number and percent of subjects initiating and completing treatment; and number and percent of subjects discontinuing treatment and discontinuing the study, further broken down by the reasons for discontinuation. Subject enrollment will also be summarized by study site. A summary of major protocol deviations will be tabulated for each cohort and cohorts combined by treatment group.

13.5 Demographics and Baseline Characteristics

Demographics and other baseline characteristics will be summarized for the subjects in the safety population. Demographic data will include age, gender, race, and ethnicity. Baseline characteristics data will include (but not be limited to) total serum IgE, FeNO, ACQ-6, and PFT (FEV1 absolute, FVC, FEV1/FVC ratio, and FEV1 %) with bronchodilator reversibility. Medical history data will include (but not be limited to) time from diagnosis of asthma to Screening, prior and current medications used for asthma control, history of biologic therapy use for asthma control, hospitalizations, and intubations.

[REDACTED]

[REDACTED]

[REDACTED]

[REDACTED]

[REDACTED]

[REDACTED]

[REDACTED]

13.7 Safety Analyses

All safety data summaries will use the safety population.

The number and percent of subjects experiencing any DLTs will be presented by cohort. A listing of DLTs will also be provided.

Adverse events will be coded using the Medical Dictionary for Regulatory Activities (MedDRA, v 20.1, or the current version) and will be graded by the investigator using the CTCAE v 5.0 or the current version. Subject incidence of TEAEs, treatment-emergent serious AEs (TESAEs), TEAEs leading to treatment discontinuation and TEAEs with an outcome of death will be summarized by SOC and preferred term (PT). Adverse events will also be further summarized by

worst severity grade and relationship to study drug. [REDACTED]

[REDACTED]

Clinical laboratory data will be summarized descriptively, these summaries will include observed values at collection time points and their changes from baseline. All laboratory parameters that can be graded using the CTCAE will be graded. For selected parameters, following summaries may be produced:

- Worst post-baseline severity grade
- Shift summary of baseline grade to worst post-baseline severity grade.

Safety evaluations may also include changes in the subject's physical examination findings, vital signs, and 12-lead ECG findings.

[REDACTED]

[REDACTED]

[REDACTED]

[REDACTED]

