This is a phase 1b, randomized, double-blind, placebo-controlled study to evaluate the safety, tolerability, PK, [REDACTED] clinical activity of EQ001, a humanized immunoglobulin G1 (IgG1) monoclonal antibody that selectively targets CD6 on T_{eff} cells, in subjects with moderate-to-severe uncontrolled asthma. The study will initially enroll up to 32 subjects in up to 4 successive dose cohorts of 8 adult subjects each (up to 10 subjects may be enrolled to achieve 8 DLT evaluable subjects). Doses of 0.8, 1.6, 2.4, and 3.2 mg/kg EQ001, or an equivalent volume of placebo, will be administered subcutaneously (SC) every 2 weeks (Q2W) for a total of 5 doses. Subjects will be randomized in a 3:1 ratio (active:placebo) to characterize the safety, tolerability, PK, PD, and clinical activity of ascending SC doses of EQ001 and to determine the maximum tolerated dose (MTD). After determination of the MTD, and at the Sponsor's discretion, the MTD cohort may be repeated to increase the number of subjects receiving the MTD to 12 and subjects in the pooled placebo cohort to 10; therefore, the total number of subjects enrolled in the study may be up to 40.

Written informed consent for study participation will be obtained before any study-related procedures or assessments are performed. All potential subjects will be screened for potential participation, and those meeting all eligibility criteria will be offered participation in the study.

The study will be conducted in the following 3 defined periods:

1. **Screening Period:** Will begin when the informed consent form (ICF) is signed. During this period, the subject will undergo baseline assessments to determine eligibility for study participation. The subject will complete an electronic diary (eDiary) to record asthma symptoms, AM and PM peak expiratory flow rate measurements, use of controller and rescue medication, nighttime awakening due to asthma and asthma-related activity limitations. The Screening Period duration will be up to 4 weeks; it will end after at least 2 weeks of baseline assessments have been conducted and all studies required to meet eligibility have been completed. If a subject meets all eligibility criteria (including documented compliance with eDiary completion, peak flow monitoring and adherence to their standard-of-care [SoC] meds), they will be enrolled into the study.

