5.1 Safety Population

The Safety Population consists of all subjects who receive any study drug. Subjects will be analyzed according to treatment actually received.

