7.1 Subject Disposition

Subject disposition data will be summarized using the Safety Population and will include the number and percent of subjects randomized, treated, and replaced. The number and percent of subjects completing treatment and study, and the number and percent of subjects discontinuing treatment and discontinuing the study, by primary reason for discontinuation. Subject enrollment will be summarized by study site. The continuous summary statistics will be presented for the follow-up duration, where the follow-up duration in weeks will be calculated as:

Follow-up duration (weeks) = (date of last contact – date of first dose of study drug + 1) / 7, rounded to 1 decimal place. The number and percent of subjects who failed screening, along with the reasons for screen failure, will be presented for all subjects who signed informed consent. By-subject listings will also be created for disposition data.

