8.1.10 Annualized Rate of Asthma Exacerbations (of any severity)

The number of asthma exacerbations will be calculated for each subject. A follow-up duration in years for each subject will be calculated as:

Follow-up duration (years) = (last contact date – date of first dose + 1) / 365.25, rounded to 2 decimal places.

The annualized rate of asthma exacerbations i.e. number of asthma exacerbation per subject year will be calculated as total number of asthma exacerbations for all subjects / total follow-up duration in years for all subjects.

Rate of asthma exacerbation will be tabulated, and a by-subject listing of all exacerbations will be created.

In addition, duration of asthma exacerbations in days is calculated as (the end date – the start date)+1. If asthma exacerbation is ongoing, the missing end date will be imputed as last known visit date. If a subject has multiple asthma exacerbations, each event will be counted separately.

The primary criterion for asthma exacerbations will also be summarized by criterion in number and frequency format. All asthma exacerbations will be included in this summary, a subject may have more than one exacerbation event.

[REDACTED]

[REDACTED]

[REDACTED]

[REDACTED]

[REDACTED]

[REDACTED]

This document is confidential.

[REDACTED]

10 Safety

All safety analyses will be performed using the Safety Population.

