A subject will be counted once at the SOC level and once at PT level. For summaries by SOC, PT, and CTCAE severity grade, a subject will be counted once at highest observed severity grade within an SOC and PT. Summaries by relatedness would be handled similar to the summaries by severity grade. Summaries by SOC and PT will be ordered by overall descending frequency of SOC and then, within a SOC, by overall descending frequency of PT.

Summaries of AEs will include:

- An overall summary providing subject incidence of the following:
 - Any TEAE
 - Any treatment-emergent serious AE (TESAE)
 - Any treatment-related TEAE
 - Any treatment-related TESAE
 - TEAE by maximum severity
 - Any TEAE leading to the end of treatment
 - Any TEAE leading to death
 - Any dose limiting toxicity (DLT)
 - [REDACTED]
- TEAEs by SOC and PT
- TEAEs Related to Study Drug
- TESAEs by SOC and PT

This document is confidential.

[REDACTED]

- TEAEs with Severity Grade ≥ 3 by SOC and PT
- TEAEs by SOC, PT and Worst Severity Grade
- TESAEs Related to Study Drug
- TEAEs Leading to End of Treatment by SOC and PT
- TEAEs Leading to Death by SOC and PT
- Dose Limiting Toxicities by SOC and PT

A by-subject listing of AE data will also be created. In general, adverse events occurring within 30 days after last dose of study drug will be included in the AE summaries but all AEs will be included in the listings. AEs occurring before start of study treatment will be included in the data listings but will not be included in the summary tables of AEs.

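### The planned DLT percentage does not match the DLT-evaluable, Day 1–29 basis of the design, so the reported rate per dose can be off in either direction

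*Protocol*

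**What the plan says.** - **Cohort size.** Protocol 2.1 and 7.1 and SAP 3.2 plan cohorts of 8, randomized 3:1, and add that "up to 10 subjects may be enrolled to achieve 8 DLT evaluable subjects".
- **Window.** The protocol synopsis has the Data Review Committee (DRC) convene when 2 subjects in one cohort have a DLT in the assessment period, given as Study Days 1–29.
- **Definition, protocol.** The synopsis takes drug-related events of CTCAE Grade 3 or higher, leaves out those attributed to the underlying asthma, and has a separate rule for lymphopenia.
- **Definition, SAP.** SAP 10.3 repeats the grade and lymphopenia rules. It states neither the asthma exclusion nor a window. Its AE summaries generally run to 30 days after the last dose.
- **Denominator.** Protocol 13.7 opens with "All safety data summaries will use the safety population" and then says "The number and percent of subjects experiencing any DLTs will be presented by cohort". SAP Section 10 opens with "All safety analyses will be performed using the Safety Population". SAP 5.1 defines the set: "The Safety Population consists of all subjects who receive any study drug".
- **DLT tables in the SAP.** SAP 10.3 lists DLT incidence in the overall AE summary and a table titled "Dose Limiting Toxicities by SOC and PT". Neither has its own denominator.
- **Replaced subjects.** The disposition table in SAP 7.1, also on the Safety Population, "will include the number and percent of subjects randomized, treated, and replaced".
- **Changes.** SAP Section 12 declares no departure from the protocol's analyses.

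**The concern.** Allowing 10 to be enrolled so that 8 are evaluable accepts that some enrolled subjects cannot inform the DLT assessment. One example is a subject who is dosed once and leaves before Day 29 without a DLT. Under the Safety Population rule that subject counts as a full non-event. Under the sizing rule the subject is set aside and another may be enrolled.

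The numerator differs as well. The cohort decision looks at Days 1–29, whereas the SAP's tables can take in events from the whole treatment and follow-up period. They can also take in events that the protocol's definition would exclude because of their link to asthma.

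What is at stake is the DLT rate shown per dose in the final report. Finding the maximum tolerated dose (MTD) is a stated purpose of the trial, and a reader will take the tabulated percentage as the DLT rate that goes with the escalation rule. As planned, it differs from that rate in denominator, time window and event definition.

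**Working it through.** **1. The plan's own sizes.** A cohort of 8 at 3:1 has 6 on EQ001 and 2 on placebo. Four cohorts give 4 × 8 = 32 subjects (24 EQ001, 8 placebo). One repeated MTD cohort adds 6 + 2, giving 40 in total, 30 on EQ001, 10 on placebo and 12 at the MTD. All four agree with the protocol. The documents state no DLT rate, so there is none to reproduce.

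**2. Denominators.** A cohort enlarged to 10 at 3:1 has 10 × 3/4 = 7.5, so 7 or 8 on EQ001. Assumption: 6 of these are DLT-evaluable, and the other 1 or 2 were dosed, were not evaluable and had no DLT.

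**3. Effect of the denominator alone.** The rate is x/n, with exact (Clopper-Pearson) 95% intervals:

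| DLTs | Evaluable, n = 6 | Safety Population, n = 7 | Safety Population, n = 8 |
|---|---|---|---|
| 1 | 16.7% (0.4 to 64.1) | 14.3% (0.4 to 57.9) | 12.5% (0.3 to 52.7) |
| 2 | 33.3% (4.3 to 77.7) | 28.6% (3.7 to 71.0) | 25.0% (3.2 to 65.1) |
| 3 | 50.0% (11.8 to 88.2) | 42.9% (9.9 to 81.6) | 37.5% (8.5 to 75.5) |

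The rate is multiplied by 6/7 = 0.86 or 6/8 = 0.75. If every dosed EQ001 subject is evaluable, the factor is 1 and nothing changes.

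**4. Effect of the window.** The last planned dose is on Day 57, and 57 + 30 = Day 87, so the SAP's AE window covers all follow-up to the Day 85 visit. Suppose one EQ001 subject has a DLT within Days 1–29 and another has one later. The design basis gives 1/6 = 16.7%. The SAP basis gives 2/8 = 25.0%, or 2/7 = 28.6%. The reported figure is now the higher one. A drug-related Grade 3 event that is also attributed to asthma would act the same way, since the SAP's definition does not exclude it.

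**5. Effect on the DRC trigger.** The trigger is a count of 2 in a cohort. No denominator enters it, so it is unchanged.

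**The case against.** The strongest reply is that a count of all DLTs among all dosed subjects is a legitimate safety summary. The synopsis attaches the Day 1–29 window to the cohort trigger, and its list of reasons to stop dosing a subject includes a DLT at any time in the treatment period. A full-period table is therefore coherent. Counts, a DLT listing and the number of replaced subjects will also be reported, so readers see more than a bare percentage. This stands, and it is why the Safety Population table should stay. It does not supply a rate on the basis the design uses.

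Redaction is the second reply. The protocol refers to Section 7.2.1 for the DLT definition, but the visible text there has none. Section 13.3.3 is not visible, and text after SAP 5.3 is blacked out. A definition of DLT-evaluable, or even an analysis set, may be there. It cannot be said that none exists. What can be said is that two unredacted rules put all safety summaries on the Safety Population, and that no visible DLT table is exempted.

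A reader might infer three stronger points that the documents do not support:

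- **That the rate will be diluted.** Enlargement is optional. Dilution needs at least one EQ001 subject who was dosed, not evaluable and free of DLT, and a subject who was never dosed is outside the Safety Population. Step 4 shows that the net error can also be upward.
- **That this percentage is the main support for the MTD.** The trigger is a count followed by DRC judgement. The MTD rests on the whole of the safety, tolerability, PK, PD and clinical activity data. The SAP's analyses follow database lock, while DRC reviews use earlier data snapshots. No visible rule uses a DLT percentage.
- **That presentation by cohort puts placebo subjects in the denominator.** Protocol 13.1 splits summaries by cohort and treatment group, and SAP 6.1 gives pooled placebo and each EQ001 dose their own columns.

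**Conclusion.** The point holds as a mismatch between the reported DLT rate and the design's own DLT basis. It concerns the denominator (all dosed against DLT-evaluable), the window (whole study against Days 1–29) and the event definition (with or without the asthma exclusion).

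The denominator alone can lower the rate by a factor of at most 0.75 in a cohort of 10. That assumes 6 evaluable EQ001 subjects and two extra who are both on EQ001, dosed, non-evaluable and DLT-free. The window and definition can raise the rate, so the sign of the net error is not known in advance. Both effects are small beside the intervals at these sample sizes. Escalation decisions under the stated trigger do not change. It is still worth correcting: the mismatch comes from stated rules, and the remedy is cheap.

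**What to change.** In SAP 10.3 and Protocol 13.7:

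1. Add a table of subjects with a DLT in Study Days 1–29, by EQ001 dose and for pooled placebo, with DLT-evaluable subjects as the denominator.
2. Point to where DLT-evaluable is defined. That definition should say whether a subject who has a DLT and then leaves early counts as evaluable.
3. Reconcile the DLT definition in SAP 10.3 with the one in the protocol synopsis, on both the window and the asthma exclusion. If a difference is intended, list it in SAP Section 12.
4. Keep the Safety Population table and the listing of all events meeting DLT criteria as a supplement, labelled with their time window.

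The cost is one subject-level flag, one table and a few lines of text. Conduct, dosing and sample size are untouched. The downside is that the DLT percentages may look slightly less favourable where dosed subjects were replaced.
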